9.2	Sample size, accrual time and study duration:	30
9.3	Statistical analysis:.....	31
10.	STUDY INVESTIGATORS	32
11.	DATA PRIVACY AND SECURITY	32
12.	REFERENCE LIST	34
13.	APPENDIX	38
13.1	Recruitment Communications	38
13.2	Phone Screening Forms and Questionnaires.....	38
13.3	Consent Form	38
13.4	Baseline and Post-Intervention Questionnaires.....	38
13.5	Physical Activity Assessments and Exercise Intervention Materials	38
13.6	Nutrition Assessments and Intervention Materials.....	38
13.7	Chemotherapy Toxicity, Side Effects, and Injury History Forms and Email.....	38
13.8	Anthropometric Measurements and Blood Draw Procedures	38
13.9	Usual Care Handout	38
13.10	Thank You Card Text.....	38

PROTOCOL SUMMARY

Protocol Version Date: 2/11/2022

Principal Investigators: Multiple PI: [name] DrPH, Kaiser Permanente of Northern California (Corresponding PI); [name], Pennsylvania State University; [name], Dana-Farber Cancer Institute

PROTOCOL TITLE

1. Full Title: FORCE: Focus on Reducing Dose-Limiting Toxicities in Colon Cancer with Resistance Exercise

STUDY SPONSORSHIP

- 1. Funding Sponsor:** NATIONAL CANCER INSTITUTE/NIH
- 2. Primary Sponsor:** Kaiser Permanente of Northern California – [name]

PROTOCOL ABSTRACT

FORCE is a randomized home-based resistance training/strength training (RT) intervention study for Stage II and III colon cancer patients undergoing chemotherapy.

Participants will be 180 newly diagnosed Stage II and III colon cancer patients from Kaiser Permanente of Northern California (KPNC), the Penn State Cancer Institute (PSCI), and the Dana Farber Cancer Institute (DFCI). The intervention will begin by the third visit for adjuvant chemotherapy and continue exercise through the completion of post-operative chemotherapy. Specifically, we will examine between group differences for RT versus waitlist control for chemotherapy outcomes including dose delays, dose reductions, early stoppage and Grade 3 and 4 toxicities. We will also study changes in muscle mass (MM) and changes in specific inflammatory markers (e.g. CRP, IL-6 and TNF-RII) as potential markers of change in response to RT. To determine effects of change of MM on chemotherapy-specific drug clearance, we will examine the impact body composition changes on the pharmacokinetics (PK) of 5-FU and oxaliplatin, two of the most commonly used drugs for colon cancer.

OBJECTIVES

1. Primary Objective:

To examine differences in dose reductions, dose delays and early stoppage for chemotherapy and the total combined number of moderate and severe chemotherapy-associated toxicities between intervention group and waitlist controls.

2. Secondary Objectives:

- a. To examine specific inflammatory markers (e.g. CRP, IL-6, TNF- α receptor II [TNF-RII]) in relation to baseline MM and fat mass (FM) and examine differences in changes in inflammatory markers between intervention group and waitlist controls. Inflammatory markers and body composition will be measured pre and post intervention.
- b. To examine the impact of RT induced body composition changes on the pharmacokinetics (PK) of 5-FU and oxaliplatin between baseline and 4 months of RT.

3. d3 Creatine Objectives

- a. To test whether resistance training during chemotherapy (v. control) increases d3 creatine muscle mass at 6 months.

- b. To evaluate the association of d3 creatine muscle mass with changes in functional status and strength during chemotherapy.
- c. To evaluate the association of d3 creatine muscle mass with chemotherapy toxicity and relative dose intensity.
- d. To evaluate the association of d3 creatine muscle mass with cancer-related biomarkers, including inflammation, CEA levels and cardiometabolic risk factors.

BACKGROUND

1.1 Colon cancer epidemiology and prognosis by stage:

Colorectal cancer is the 4th most common in the United States, with an estimated 134,490 individuals being diagnosed in 2016, 71% located in the colon (versus rectum)². Unfortunately, more than 49,190 individuals die from the disease annually, making colorectal cancer the second leading cause of cancer death in the United States. Surgery is the primary modality of management for colon cancer, and a ‘curative intent’ resection occurs in 80–85% of patients with non-metastatic disease (stages I-III). The benefit of adjuvant therapy has been consistently shown in multiple clinical trials, although the 5-year disease free survival for stage III disease is only 70%³.

1.2 Adjuvant chemotherapy and dosing:

Beginning in 1990, an NCI expert panel recommended 5-fluorouracil (5-FU) and leucovorin (LV) as adjuvant therapy for patients with stage III colon cancer⁵. While initial studies tested a longer duration of treatment, the current standard is 6 months of therapy. An oral form of 5-FU, called capecitabine, has also demonstrated noninferiority as an alternative to IV 5-FU⁶. Select stage II patients, based on recurrence risk, are considered for adjuvant therapy as well. Further trials demonstrated a modest, but statistically significant, benefit to adding oxaliplatin to 5-FU/LV. The most common regimen is a 3 drug infusional combination called FOLFOX (5-FU/LV and oxaliplatin), now standard treatment for most stage III patients, considered in some stage II patients⁴ as well as in stage IV/metastatic disease patients. Substitution of capecitabine for infusion 5-FU and leucovorin is another treatment regimen (CAPOX). Dosing of 5-FU/LV, capecitabine or FOLFOX is based on a standard formula that incorporates a patient’s height and weight into a metric called, body surface area (BSA)⁷. Recommended milligrams per BSA were derived from trials testing for dose limiting toxicities (DLT), typically defined as severe (grade III or IV based on the NCI Common Toxicity Criteria [CTC] scale). While a standard starting dose is defined for each treatment option, many patients will still derive significant toxicities (Table 1). Issues with BSA dosing include the use of absolute weight without consideration of body composition or physiologic measures relevant for drug metabolism and disposition, such as renal and hepatic function. **Dosing based on BSA is limited in ability to reduce inter-patient variability in a drug’s volume of distribution⁸.** Various drug elimination processes (e.g. metabolic breakdown or excretion) account for inter-patient variability in pharmacokinetics to a large degree⁸. Body composition (i.e. adipose tissue and muscle mass)⁹ is another factor influencing pharmacokinetics and may predict toxic reactions to certain chemotherapy regimens^{10;11}.

Table 1. Select Toxicities associated with adjuvant therapy⁴

Toxicity	5-FU/LV		FOLFOX	
	Any Grade	Grade 3/4	Any Grade	Grade 3/4
Neutropenia	40%	5%	79%	41%
Low platelets	19%	<1%	77%	2%
Nausea	61%	2%	74%	5%
Diarrhea	48%	7%	56%	11%
Neuropathy	16%	<1%	92%	12%

1.3 Toxicities of adjuvant therapy:

All 4 adjuvant therapy regimens have potential for multiple toxicities, including but not limited to gastrointestinal (e.g. nausea, emesis, diarrhea, abdominal cramping or discomfort), bone

marrow suppression (i.e. lowering white blood cells and thus immune system or platelets increasing bleeding risk), and fatigue and anorexia symptoms (Table 1). Oxaliplatin can lead to cold-induced and/or cumulative peripheral neuropathy, manifested as numbness, pins and needles, or pain in hands and feet, which can impact function.

1.4 Pharmacokinetics of 5-FU and oxaliplatin are altered by body composition:

Cytotoxic agents, such as fluoropyrimidine and oxaliplatin, are considered narrow therapeutic index drugs, where small changes in drug exposure can greatly impact clinical efficacy and toxicity. 5-FU is hydrophilic, but widely distributed through active transport¹². It undergoes extensive metabolism, primarily through dihydropyrimidine dehydrogenase (DPYD), variants of which have been associated with increased risk of toxicity to 5-FU¹³. On the basis of these considerations, 5-FU clearance (CL) and volume of distribution (V) are likely related to body composition. Gusella *et al.* studied the PK of adjuvant 5-FU (425 mg/m² IV bolus) in 34 colorectal cancer patients¹⁴ and determined that CL was significantly correlated with sex and fat free mass (FFM), while V was correlated with sex and Total Body Water (TBW). Overall, they concluded that CL of 5-FU was better predicted by FFM and TBW than by Body Surface Area (BSA)¹⁴. Thus, clearance of 5-FU is expected to increase (i.e. exposure decrease) in individuals with a higher FFM.

Body composition is also known to impact the PK of oxaliplatin. Oxaliplatin is eliminated renally, with clearance similar to glomerular filtration rate¹⁵. Quinney *et al.*¹⁶ have previously reported that obesity is associated with an increased GFR as measured by clearance of iohexol. Thus, it is expected that oxaliplatin clearance may be increased in individuals with more adiposity and because it is also highly lipophilic, may lead to increased distribution in individuals with higher FM/MM ratios. In a population PK analysis of ultrafilterable oxaliplatin in 56 adults with metastatic disease, both CL and V were associated with bodyweight and individuals with higher body weights had larger exposure (AUC) to oxaliplatin¹⁷. To our knowledge, the effect of MM measured by DXA and change in body composition over time on PK of these drugs has not been examined.

1.5 Low muscle mass increases dose limiting toxicity:

The effect of low MM on chemotherapy treatment in several individual studies of different chemotherapy drugs and different cancer types have been explored. Cancer patients with identical BSA (i.e. 2.00 m²) are highly variable in MM (range 30–70 kg)¹⁸ and it has been hypothesized that low MM may result in a smaller tissue volume for distribution of cancer therapies, with potentially lower capacity for metabolism and clearance of drugs, leading to enhanced toxicity.

1.6 Dose limiting toxicities are associated with poorer prognosis:

Several studies across different cancers have demonstrated that either dose reductions or dose delays are associated with poorer overall survival (OS) or progression-free survival (PFS). Most relevant to this current study is a study that was designed to evaluate the impact of relative dose intensity (RDI), dose reduction, and schedule modification on outcomes in patients with

metastatic colorectal cancer (mCRC). Pooled datasets from two previous phase II trials of FOLFIRI (CCOG-0502; n=36) and mFOLFOX6 (CCOG-0704; n=30) in patients with mCRC were analyzed retrospectively. The median RDIs of irinotecan in FOLFIRI and oxaliplatin in mFOLFOX6 were 80 and 79%, respectively. Higher RDI of irinotecan in FOLFIRI was associated with significant improvements in PFS (9.9 vs. 5.6 months, $P < 0.01$) and OS (26.7 vs. 12.9 months, $p=0.01$) and was the only independent factor associated with PFS (hazard ratio [HR] 8.48, $p < 0.01$). Time delays of oxaliplatin was the only independent factor associated with PFS (HR 2.74, $p=0.04$)²¹. Numerous studies of women receiving chemotherapy treatment for ovarian cancer have also demonstrated that RDI, dose delays and dose reductions in chemotherapy regimens impact PFS and OS. In one of the largest multi-center retrospective studies of 325 women with FIGO stage III-IV epithelial ovarian cancer treated postoperatively with multi-agent intravenous chemotherapy between 1995 and 2009²², delivered RDI <85% (hazard ratio [HR]=1.71; $p=0.003$) was associated with reduced OS.

1.7 Previous exercise interventions were successful in preventing dose reductions and improving chemotherapy completion rates:

To our knowledge, only a few previous studies have examined the effect of exercise on chemotherapy completion rates or in preventing dose reductions. In the most recent large study, a moderate to high-intensity, combined supervised resistance and aerobic exercise program (OnTrack) was compared to usual care (UC) in 230 breast cancer patients scheduled to undergo chemotherapy. Performance-based and self-reported outcomes were assessed before random assignment, at the end of chemotherapy, and at the 6-month follow-up. Those randomized to OnTrack required less chemotherapy dose adjustments ($p=.002$) had less nausea and vomiting ($p=.031$) compared with UC. Table 2 shows rates and reasons for chemotherapy dose reductions²³. Similar non-significant results were observed in another small (n=33) study of CRC patients in Europe²⁴, however the sample size was too small for definitive results. In a second study of 242 breast cancer patients²⁵ those randomized to supervised resistance training during chemotherapy compared to usual care resulted in improved chemotherapy completion rate ($p=.033$). In a third trial of 30 women with recurrent ovarian cancer²⁶, a 12 week combined supervised and home-based exercise intervention during chemotherapy demonstrated that participants who completed the intervention had a higher relative dose intensity than non-completers ($p=0.03$)^{25,26}. While three of the studies collectively demonstrate positive effects of exercise training during chemotherapy on completion rates and/or prevention of dose reductions in other cancers, only one small trial with inadequate power studied these effects in colon cancer patients, demonstrating a need to examine this in a group who experience significant DLT and a high prevalence of sarcopenia at diagnosis.

1.8 Inflammation, muscle mass and exercise:

Although the development of muscle wasting involves multiple contributors including neuropeptides, hormonal mediators, tumor- or pathogen-derived compounds, as well as various cytokines, the presence of inflammatory processes represents the primary requirement for the alterations in muscle protein synthesis and breakdown²⁷. Recently, this observation was confirmed in a CRC cohort. Richard et al. reported an association between low skeletal MM index measured on CT scans and increased acute inflammatory response (i.e. high C-reactive protein and low albumin)²⁸. In another study of 763 patients diagnosed with CRC undergoing elective surgical resection, multivariate logistic regression analysis showed that high neutrophil/lymphocyte ratio (NLR) (odds ratio [OR]=1.78 (95% confidence interval [CI]: 1.29-2.45), $p < 0.001$) and low albumin (OR=1.80 [95% CI: 1.17-2.74], $p=0.007$) were independent predictors of reduced muscle mass²⁹. A plethora of studies have investigated the role of the main inflammatory players in muscle wasting, such as tumor necrosis factor- α (TNF- α), interleukin-6 (IL-6), interleukin-1 (IL-1) and interferon- γ (IFN γ). These pro-inflammatory cytokines act directly or potentiate each other's actions at two key metabolic control points: the activation of ubiquitin-proteasome system³⁰ and inhibition of Akt/mTOR pathways³¹, promoting protein

degradation as well as resistance to the anabolic actions, and ultimately leading to muscle loss. Several studies have now demonstrated that exercise reduces inflammation, through multiple mechanisms³². Specific to RT, an acute transient local *increase* in IL-6 is observed, which in turn results in a rise in anti-inflammatory markers locally to combat this rise, such as IL-10 and IL-1A, blunting the release of further inflammatory factors. This local effect then stimulates pro- and anti-inflammatory molecule secretion by other tissues, thus augmenting levels of systemic inflammation³³. In cancer survivors the 12-week RT intervention in breast cancer survivors compared to relaxation control (n=103), blunted the marked rise in systemic levels of inflammation observed in the control group (IL-6, $p=0.01$ and IL6: IL-1ra ratio, $p=0.02$)³⁴.

1.9 Summary:

Since reductions in dose intensity of chemotherapy (both dose reductions and/or not completing planned number of treatments) are associated with lower survival in many cancers, identifying ways to maintain dose intensity are of tremendous clinical significance. Sarcopenia or low MM is a highly prevalent and an occult problem among newly diagnosed colon cancer patients and is associated with DLT. RT is known to increase MM, and increases in MM could reduce DLT with a potential impact on survival. This study may also provide evidence for consideration of dosing based on body composition. This study will fill many existing gaps in our understanding of body composition, RT and DLT.

2. OBJECTIVE

2.1 Primary Objective:

To examine differences in dose reductions, dose delays and early stoppage for chemotherapy and the total combined number of moderate and severe chemotherapy-associated toxicities between intervention group and waitlist controls.

2.2 Secondary Objectives:

2.2.1 Examine specific inflammatory markers (CRP, IL-6, TNF- α receptor II [TNF-RII]) in relation to baseline MM and FM and examine differences in changes in inflammatory markers between intervention group and waitlist controls.

2.2.2 Examine the impact of intervention versus control and RT-induced body composition changes on the pharmacokinetics [PK] of 5-FU and oxaliplatin between baseline and 4 months of RT.

2.3 d3 Creatine Objectives:

2.3.1 Test whether resistance training during chemotherapy (FORCE intervention group v. control) increases d3 creatine muscle mass at 6 months.

2.3.2 Evaluate the association of d3 creatine muscle mass with changes in functional status and strength during chemotherapy.

2.3.3 Evaluate the association of d3 creatine muscle mass with chemotherapy toxicity and relative dose intensity.

2.3.4 Evaluate the association of d3 creatine muscle mass with cancer-related biomarkers, including inflammation, CEA levels and cardiometabolic risk factors.

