2. Study staff will then record the adherence of the patients to the exercise regimen and the pattern of sessions with regard to time between sessions, as well as any medical complications that prevent sessions from happening.

Intervention Goals:

Progressively higher weights for resistance training exercises conducted twice weekly throughout intervention) to achieve a 1-kg increase in lean body mass by the end of the intervention.

Intervention Standardization:

All exercise professionals will participate in a multi-day workshop. During this workshop, procedures of the intervention will be explained, and case studies will be presented and practiced. There will be monthly conference calls including all exercise professionals across sites, to monitor and discuss progress, problems and to monitor fidelity of the protocol. Telephone calls to intervention participants to encourage adherence will be scripted.

3.9 Enhanced safety procedures due to COVID-19:

As a result of COVID-19, exercise professionals will adhere to strict safety procedures when meeting with participants for the in person exercise sessions. Enhanced safety procedures include:

- phone screening before visits with COVID-19 script (Appendix 13.2.6),
- temperature checking when entering a clinical facility (KP only),
- both exercise professional and participant wearing face masks,
- frequent hand washing and hand sanitizing,
- maintaining a 6 ft distance when possible,
- frequently wiping down surfaces and equipment with disinfectant wipes, and
- any other appropriate precautions as required by local clinic and hospital procedures.

DFCI exercise professionals will be following DFCI COVID-19 policy for patients and staff while in the building.

3.10 Intervention for the waitlist controls:

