Pharmacokinetics: As 5-FU is known to undergo nonlinear disposition, compartmental modeling will be conducted using nonlinear mixed effects analysis with NONMEM (Icon Development Solutions, Hanover MD). NONMEM allows for simultaneous estimation of fixed-effects values (e.g. CL and V) and random-effects values (e.g. inter-individual, inter-occasional, and residual unexplained variability). Previous models of 5-FU and oxaliplatin²⁸ have been reported and will serve as a basis for development of the structural model. The final structural (e.g. 1- vs. 2-compartment) and error models (e.g. additive or proportional) will be chosen based on minimization of the objective function value (OFV, $-2 \log$ likelihood) and evaluation of diagnostic plots generated in R. During the covariate selection process, various measures of body composition (e.g. MM, MM/FM ratio) will be compared to identify the contribution of these parameters to PK variability in colon cancer patients. Pre- and post-intervention PK parameters (e.g. CL, V) will be compared using a paired t-test.

9.3.3 d3 creatine endpoints:

We will first assess the distribution of the baseline covariates by FORCE randomization arm. Most outcomes will be treated as continuous variables and we will fit linear regression models (e.g., for the continuous outcomes such as change in d3 creatine muscle mass, SPPB and SF-36 score, grip strength, relative dose intensity, and values of inflammatory markers, CEA and cardiometabolic risk factors). We will assess departures from regression model assumptions primarily by diagnostic plots of residuals, with attention to detection of non-constant variance of errors and detection of outliers that may indicate the need for a variance stabilizing transformation of the dependent variable. In secondary analyses, when considering outcomes dichotomously, we will fit logistic regression models (e.g., for abnormal CEA values).

Aim 1 is a randomized comparison of the FORCE resistance training intervention to the waitlist control. Analyses in Aims 2-4, however, are subject to confounding. Our *a priori*

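### Neither planned PK analysis estimates the effect of arm or of training-induced body-composition change that Objective 2.2.2 asks for; a single muscle coefficient would mostly reflect differences between patients

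*Protocol*

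**What the plan says.** - **Objective.** Protocol 2.2.2: "Examine the impact of intervention versus control and RT-induced body composition changes on the pharmacokinetics [PK] of 5-FU and oxaliplatin". The period runs from the start of the study to month 4. This contains two questions: a randomised comparison, and the effect of a within-patient change in body composition.
- **Covariate step.** Protocol 9.3.2 (Pharmacokinetics): "various measures of body composition (e.g. MM, MM/FM ratio) will be compared to identify the contribution of these parameters to PK variability". The model is said to allow random effects between individuals and between occasions.
- **Pre/post test.** Same section: "Pre- and post-intervention PK parameters (e.g. CL, V) will be compared using a paired t-test".
- **Restatement.** Protocol 9.1 describes the PK aim only as a pre/post comparison, without arm or body composition.
- **Data.** PK is measured on two occasions in up to 30 FOLFOX patients who also take part in the randomised comparison (3.11, 4.14). The PK cohort has a DXA at baseline and another at the second PK draw (Table 7 footnote 2, and 4.10).
- **Size of the contrasts.** Section 1.5 cites muscle mass of 30 to 70 kg among patients with the same body surface area. The intervention aims "to achieve a 1-kg increase in lean body mass by the end of the intervention" (3.8), and the cited meta-analysis found a 1.07 kg gain (3.1).
- **Sex.** Section 1.4 reports a 34-patient study in which 5-FU clearance and volume each correlated with sex as well as with a body-composition measure.

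The SAP text supplied describes the primary endpoints and does not mention PK.

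**The concern.** The objective is about change, but the planned test of change contains no body composition, and the planned use of body composition does not isolate change. A muscle covariate found in NONMEM could be a cross-sectional fact (larger-muscled patients clear drug differently) and still be the only muscle result available to answer 2.2.2. The distinction matters because section 1.9 says the study may inform dosing by body composition. A cross-sectional association can support that idea. It cannot show that gaining muscle during chemotherapy alters clearance.

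The randomised question has the same gap. No stated PK analysis contains arm, so a general shift in clearance over four months of chemotherapy would appear in the paired t-test whether or not training had any effect.

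**Working it through.** **1. The plan's own figure.** Section 9.3.4 gives 30 subjects, power .80, a mean change of 0.5 SD and two-sided alpha .05. For a one-sample test of change, power = Φ(0.5 × √30 − 1.96) = Φ(0.779) = 0.78 (0.75 with the noncentral t). The figure is reproduced to rounding by the normal approximation. It refers to one mean change over all 30 patients, pooled over arms. The stated 15% detectable change implies an SD of change of 15% / 0.5 = 30%, or 30% / √2 = 21% per occasion.

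**2. Objective against analysis.**

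| Part of 2.2.2 | Paired t-test | Covariate step |
|---|---|---|
| Intervention versus control | no arm term | no arm term stated |
| Body-composition change | no body-composition term | body composition included, no baseline/change split stated |

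**3. Where a single muscle coefficient gets its information.** Assume log clearance on two occasions, with muscle entered at both.

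Between-patient information = Σ(M − M̄)² / (s_b² + s_w²/2). Within-patient information = Σd² / (2 s_w²). Here M is a patient's mean muscle, d the change, s_b the between-patient SD and s_w the between-occasion SD of log clearance.

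Assumed, because the documents do not give them:
- muscle SD 6 to 10 kg (a 40 kg range divided by 6 or 4 gives 6.7 to 10);
- change SD 1.5 kg, with +1 kg in the training half, so the mean of d² is 1.5² + 0.5 × 1² = 2.75;
- s_b and s_w as shown in the table.

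| Muscle SD | s_b | s_w | Between = 29 × SD² / (s_b² + s_w²/2) | Within = 30 × 2.75 / (2 s_w²) | Within share |
|---|---|---|---|---|---|
| 10 kg | .25 | .25 | 30,933 | 660 | 2% |
| 6 kg | .25 | .15 | 14,156 | 1,833 | 11.5% |
| 6 kg | .40 | .15 | 6,096 | 1,833 | 23% |
| 6 kg | .25 | .10 | 15,467 | 4,125 | 21% |
| 6 kg | .40 | .10 | 6,327 | 4,125 | 39% |

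The plan's implied 21% per occasion lies within the 15% to 25% that gives 2% to 12%. If only baseline muscle is entered, the share is 0%.

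**4. Consequence.** I simulated 30 patients with s_b .25 and s_w .15 to .25, a purely between-patient slope of 1% to 2% per kg and no effect of change. The single coefficient was significant in about 17% to 95% of runs, and a separate change coefficient in about 5%. The width of that range reflects the assumptions. What it shows is that a significant single coefficient is not evidence about change.

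**5. What the separate terms deliver.**
- *Occasion term.* With a 15% drift in clearance over time and no muscle effect, a change coefficient fitted without an occasion term rejects in about 9% to 15% of runs. With the term it rejects in about 5%.
- *Precision.* The SE of the change coefficient is √(2 s_w² / Σd²). With Σd² = 82.5 it is 2.3% per kg at s_w = .15 and 3.9% at .25. With occasion and arm-by-occasion in the model, only variation within arms counts (28 × 1.5² = 63), and the SE is 2.7% to 4.5% per kg. Power for a true effect of 2% per kg is then about 7% to 11%.
- *Arm contrast.* With about 15 patients per arm (assumed from 1:1 allocation), the detectable difference is (1.96 + 0.84) × √(2/15) = 1.02 SD, or 1.06 with the t distribution. At an SD of 30% that is about 31% to 32%, against the 15% quoted for the pooled test.

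**The case against.** The best reply is that 9.3.2 leaves the parameterisation open. It names between-occasion variability, the extra DXA is timed to the second PK draw, and NONMEM can take time-varying or split covariates. That is correct. A reader might infer that the covariate step is confined to differences across patients, or that any muscle effect found will be almost wholly a between-patient one. The documents support neither. The wording covers PK variability in colon cancer patients without that limit, and the dominance of between-patient information depends on muscle entering as one coefficient and on SDs that the documents do not give. At a within-patient share near 40%, mostly is the right word. Time-varying entry alone does not remove the problem, since the shares above already allow for it.

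A reader might also infer that sex will be left out. The listed covariates are examples, so sex is not excluded; it is simply not stated. Section 1.4 supports it for 5-FU, while the oxaliplatin evidence in the background concerns body weight and adiposity. Nor does any passage say that a cross-sectional coefficient will be reported as a training effect; that is a risk, not a stated plan.

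Finally, this is an optional sub-study that 9.1 calls tertiary, and the corrected analysis has little power. That limits the weight of the point. It does not supply the missing analysis.

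**Conclusion.** The point holds in this form. Following 9.3.2 as written answers neither half of 2.2.2: arm appears in no stated PK analysis, and change in body composition is not separated from its baseline level. If muscle enters as one coefficient, most of its information is between patients: about 88% to 98% under between-occasion CVs of 15% to 25% and a between-patient CV of 25%, and about 60% in the least favourable case examined. These shares rest on assumed muscle and PK SDs, and the 30 to 70 kg spread comes from a cited study, not from this cohort.

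The primary endpoints are unaffected. The change should be made because the interpretation of 2.2.2 depends on it and the data are already being collected.

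**What to change.** In Protocol 9.3.2, or a PK section of the SAP:

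1. Enter muscle as two covariates: the baseline value, and the change from baseline at the second PK day.
2. Include an occasion term and randomised arm as arm-by-occasion. Answer intervention versus control with the arm-by-occasion effect. Read it from a fit without the change covariate, because muscle change is itself a possible result of randomisation.
3. Answer the body-composition half with the change coefficient and its interval, from the fit that also contains occasion and arm-by-occasion. Label it an exploratory within-patient association: muscle may also change for reasons other than training.
4. Report the baseline coefficient as cross-sectional only.
5. Include sex as a covariate, at least for 5-FU clearance and volume.
6. State the low power, and that the 15% in 9.3.4 refers to a change pooled over arms and not to a difference due to training.

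The cost is a few more parameters in a model with at most 30 patients, and wide intervals. No new measurement is needed: both DXA scans, sex and arm are already recorded.
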